8.8.4.3 Vital Signs

Vital sign measurements include heart rate (HR), sitting blood pressure (BP) (both systolic and diastolic), body temperature, and weight. The data will be summarized with descriptive statistics by visit and treatment group. In addition, the changes from baseline will be summarized with descriptive statistics.

Furthermore, to identify potentially clinically significant vital signs, the following criteria will be used and tabulated as a shift table by visit:

- Systolic Blood Pressure: <90 mmHg (low), 90-140 mmHg (normal), >140 mmHg (high)
- Diastolic Blood Pressure: <90 mm Hg (low), 90-100 mmHg (normal), >100 mmHg (high)

- Heart Rate: <60 beats per minute (low), 60-100 beats per minute (normal), >100 beats per minute (high).

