#### **19.6.1. Vital Sign Measurements**

Vital signs as well as changes from Baseline in vital sign measurements will be summarized with descriptive statistics for each treatment group at all applicable study visits.

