10. CHANGES IN THE PLANNED ANALYSES

There are no changes in the conduct of the study, but there are minor changes to the planned analyses.

Due to feedback received, the primary efficacy analysis was adjusted back to the original analysis. The modification to only use the non-parametric version as described in v4 of the protocol was not accepted by the agency. The original approach uses an ANCOVA analysis with the terms for treatment, analysis center, and Baseline count (and treatment-by-center interaction if the term is significant at 0.10). If the two-sided p-value for the skewness test is significant at 0.01, then the rank-transformed data will be used instead of nominal values. The original approach was accepted by the agency.

The pooling analysis described in the protocol is updated in the statistical analysis plan (SAP) to reflect the intended analysis. The protocol discusses pooling sites with five or fewer subjects enrolled in each treatment arm. Taking into consideration the randomization ratio, the SAP requires ten subjects in the active treatment arm and five subjects in the vehicle group.

As part of the pooling analysis, the treatment effect within investigational site must be investigated. The protocol states the site main effect will be examined by using a one-way analysis of variance (for lesion count variables) or a logistic regression analysis (for dichotomized IGA) with a factor of site. The SAP instead explains site will be incorporated into the primary analysis models. Change from Baseline in lesion counts will be analyzed with an ANCOVA (unranked or ranked) with factors of treatment group, investigational site and treatment group by investigational site interaction, and the respective Baseline lesion count variable as a covariate. The dichotomized primary endpoint will be analyzed with a logistic regression with factors of treatment group, investigational site and the interaction term of treatment group by investigational site.

The protocol describes repeated measures sensitivity analyses for the primary efficacy endpoints. Treatment group, analysis center and visit are listed as factors for the repeated measures analyses. In addition to these factors, the SAP includes a factor of treatment group by visit interaction.

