SOURCE: USERNAME\SPONSOR\PROJECT\JOBNAME (DATE, TIME)

Table 14.3.1.4.1: Summary of Vital Signs
(Safety Population)
(Page 4 of 5)

Diastolic Blood Pressure (mmHg)	E-BPO 5% Cream (N=xxx)	Vehicle Cream (N=xxx)
Baseline		
n	xxx	xxx
Mean	xx.x	xx.x
SD	xx.xx	xx.xx
Median	xx.x	xx.x
Min. to Max.	xx to xx	xx to xx
Week 12		
n	xxx	xxx
Mean	xx.x	xx.x
SD	xx.xx	xx.xx
Median	xx.x	xx.x
Min. to Max.	xx to xx	xx to xx
Change from Baseline		
n	xxx	xxx
Mean	xx.x	xx.x
SD	xx.xx	xx.xx
Median	xx.x	xx.x
Min. to Max.	xx to xx	xx to xx

Note: No imputation of missing values. Negative change values represent decrease from Baseline.

SOURCE: USERNAME\SPONSOR\PROJECT\JOBNAME (DATE, TIME)

Table 14.3.1.4.1: Summary of Vital Signs
(Safety Population)
(Page 5 of 5)

Heart Rate (beats/min)	E-BPO 5% Cream (N=xxx)	Vehicle Cream (N=xxx)
Baseline		
n	xxx	xxx
Mean	xx.x	xx.x
SD	xx.xx	xx.xx
Median	xx.x	xx.x
Min. to Max.	xx to xx	xx to xx
Week 12		
n	xxx	xxx
Mean	xx.x	xx.x
SD	xx.xx	xx.xx
Median	xx.x	xx.x
Min. to Max.	xx to xx	xx to xx
Change from Baseline		
n	xxx	xxx
Mean	xx.x	xx.x
SD	xx.xx	xx.xx
Median	xx.x	xx.x
Min. to Max.	xx to xx	xx to xx

Note: No imputation of missing values. Negative change values represent decrease from Baseline.

SOURCE: USERNAME\SPONSOR\PROJECT\JOBNAME (DATE, TIME)

Table 14.3.1.4.2: Shift Table of Vital Signs
(Safety Population)

	E-BPO 5% Cream (N=xxx)			Vehicle Cream (N=xxx)		
Systolic Blood Pressure (mmHg)	Week 12			Week 12		
Baseline	<90 mmHg	90-140 mmHg	>140 mmHg	<90 mmHg	90-140 mmHg	>140 mmHg
<90 mmHg	xx (xx.x%)	xx (xx.x%)	xx (xx.x%)	xx (xx.x%)	xx (xx.x%)	xx (xx.x%)
90-140 mmHg	xx (xx.x%)	xx (xx.x%)	xx (xx.x%)	xx (xx.x%)	xx (xx.x%)	xx (xx.x%)
>140 mmHg	xx (xx.x%)	xx (xx.x%)	xx (xx.x%)	xx (xx.x%)	xx (xx.x%)	xx (xx.x%)
Diastolic Blood Pressure (mmHg)	Week 12			Week 12		
Baseline	<90 mmHg	90-100 mmHg	>100 mmHg	<90 mmHg	90-100 mmHg	>100 mmHg
<90 mmHg	xx (xx.x%)	xx (xx.x%)	xx (xx.x%)	xx (xx.x%)	xx (xx.x%)	xx (xx.x%)
90-100 mmHg	xx (xx.x%)	xx (xx.x%)	xx (xx.x%)	xx (xx.x%)	xx (xx.x%)	xx (xx.x%)
>100 mmHg	xx (xx.x%)	xx (xx.x%)	xx (xx.x%)	xx (xx.x%)	xx (xx.x%)	xx (xx.x%)
Heart Rate (beats/min)	Week 12			Week 12		
Baseline	<60 bpm	60-100 bpm	>100 bpm	<60 bpm	60-100 bpm	>100 bpm
<60 mmHg	xx (xx.x%)	xx (xx.x%)	xx (xx.x%)	xx (xx.x%)	xx (xx.x%)	xx (xx.x%)
60-100 mmHg	xx (xx.x%)	xx (xx.x%)	xx (xx.x%)	xx (xx.x%)	xx (xx.x%)	xx (xx.x%)
>100 mmHg	xx (xx.x%)	xx (xx.x%)	xx (xx.x%)	xx (xx.x%)	xx (xx.x%)	xx (xx.x%)

Note: No imputation of missing values.

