			xxxx xxxxx	xxxxxxxx	xxxx xxxx xxxxxx xxxxxxxxxxxxxxxx xxxxxxxxxxxxxxxx xxxxxxxxxxxxxxxx	xxx xxx xxx xxx xxx xxx	xxx xxxxxxxxxxx xxx xxxxxxxxxxx xxx xxxxxxxxxxx
xxxxxx	xxxx	xxxxxxxx	xxxxxx	xxxxxxxx	xxxx xxxx xxxxxx xxxxxxxxxxxxxxxx xxxxxxxxxxxxxxxxxxxxxxxxxxxx xxxxxxxxxx	xxxxxx xxxxxx xxxxxx xxxxxxxxxx xxxxxxxxxxxx xxxxxx xxxxx xxx xx xxxxxxxxxx xx xxxxx xxxxxxx	
			xxxx xxxxx	xxxxxxxx	xxxx xxxx xxxxxx xxxxxxxxxxxxxxxx xxxxxxxxxxxxxxxx xxxxxxxxxxxxxxxx	xxx xxx xxx xxx xxx xxx	xxx xxxxxxxxxxx xxx xxxxxxxxxxx xxx xxxxxxxxxxx

SOURCE: USERNAME\SPONSOR\PROJECT\JOBNAME (DATE, TIME)

Listing sorted by Subject, Visit Number, and Body System (in order presented on eCRF).

Listing 16.2.8.3: Vital Signs
Treatment Arm
(Page xx of yy)

Subject	Age/Sex	Eval	Visit	Date of Assessment	Vital Sign	Result	Units
xxxxxx	xxxx	xxxxxxxx	xxxxxxxx	xxxxxxxx	xxxxxxxx xxxxx xxxxxxxx xxxxx xxxx xxxxxx xxxxxxxxxxxxx xxxx xxxxxxxx xxxxx xxxxxxxx xxxxxxxxxxxxx xxxxxx	xx xx xxxxx xx xxx xxxxx xxx	xxxx xxxxxxxxxx xx xxxxxxxxxxxxx xxxxx x xx
			xxxx xxxxx	xxxxxxxx	xxxxxxxx xxxxx xxxxxxxx xxxxx xxxx xxxxxxxxxxxxx xxxx xxxxxxxx xxxxx xxxxxxxx xxxxxxxxxxxxx	xx xxx xxxx xxx xxx xx	xxxx xxxxxxxxxxxxx xxxxx x
xxxxxx	xxxx	xxxxxxxx	xxxxxxxx	xxxxxxxx	xxxxxxxx xxxxx xxxxxxxx xxxxx xxxx xxxxxx xxxxxxxxxxxxx xxxx xxxxxxxx xxxxx xxxxxxxx xxxxxxxxxxxxx xxxxxx	xx xx xxx xx xx xx xxx	xxxx xxxxxxxxxx xx xxxxxxxxxxxxx xxxxx x xx
			xxxx xxxxx	xxxxxxxx	xxxxxxxx xxxxx xxxxxxxx xxxxx xxxx xxxxxxxxxxxxx xxxx xxxxxxxx xxxxx xxxxxxxx xxxxxxxxxxxxx	xxx xxxx xxx xxxx xxx xxxx xxx xxxx xxx xxxx	

SOURCE: USERNAME\SPONSOR\PROJECT\JOBNAME (DATE, TIME)

Listing sorted by Subject, Visit Number, and Vital Sign (in alphabetical order).

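### The SAP classes every diastolic pressure below 90 mmHg as low and only 90-100 mmHg as normal, so the diastolic shift panel cannot pick out low values

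*SAP*

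**What the plan says.** SAP Section 8.8.4.3 (Vital Signs) introduces three-way classes for blood pressure and heart rate and gives their purpose: "to identify potentially clinically significant vital signs, the following criteria will be used and tabulated as a shift table by visit". The two blood pressure lines are:

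- "Systolic Blood Pressure: <90 mmHg (low), 90-140 mmHg (normal), >140 mmHg (high")
- "Diastolic Blood Pressure: <90 mm Hg (low), 90-100 mmHg (normal), >100 mmHg (high")

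The shell headed "Table 14.3.1.4.2: Shift Table of Vital Signs" carries the diastolic cut-points into its rows and columns (below 90, 90-100, above 100 mmHg). It prints the numeric ranges without the words low, normal and high.

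No other text corrects the diastolic line. Protocol Section 19.6.1 sets no classes: "Vital signs as well as changes from Baseline in vital sign measurements will be summarized with descriptive statistics". SAP Section 10 opens with "There are no changes in the conduct of the study, but there are minor changes to the planned analyses" and does not mention vital-sign limits in what follows.

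**The concern.** Systolic and diastolic pressure have been given the same lower limit of normal. Within one reading the diastolic value is below the systolic, so a shared lower limit cannot describe the normal range of both. The result is a very wide bottom class for diastolic pressure, with no boundary inside it.

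What is at stake is whether the panel does the job the SAP gives it. If every reading below 90 mmHg falls in one class, the panel cannot count patients with a low diastolic value, nor show a patient whose pressure drops within that class. SAP Section 7.2 lists vital signs among the safety assessments, although the safety endpoints in the protocol (Synopsis and Section 8) do not include them.

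**Working it through.** There is no sample size, power or alpha figure to reproduce. The check applies the stated limits.

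**Inputs.** The class limits come from SAP Section 8.8.4.3: systolic normal 90-140, diastolic normal 90-100, heart rate normal 60-100. The shift layout comes from the Table 14.3.1.4.2 shell (three Baseline classes by three Week 12 classes). Timing comes from the protocol: vital signs are recorded at the physical examination (Section 13.7), which the flow chart schedules at Baseline and Week 12.

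**Step 1: do the two lines fit together?** Count the whole-mmHg diastolic values that are in 90-100 and also below the systolic value.

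| Systolic (mmHg) | Diastolic values classed normal | Count |
|---|---|---|
| 90 | none | 0 |
| 91 | 90 | 1 |
| 95 | 90-94 | 5 |
| 99 | 90-98 | 9 |

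A patient at the SAP's own lower limit of normal systolic pressure is therefore always low on diastolic.

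**Step 2: width of the normal band.** Systolic 140 - 90 = 50 mmHg; diastolic 100 - 90 = 10 mmHg; heart rate 100 - 60 = 40 beats per minute.

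**Step 3: what the shift panel shows.**

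| Baseline to Week 12 (mmHg) | Change | Classes | Shift shown? |
|---|---|---|---|
| 88 to 50 | -38 | <90 to <90 | no |
| 85 to 55 | -30 | <90 to <90 | no |
| 92 to 88 | -4 | 90-100 to <90 | yes |
| 88 to 92 | +4 | <90 to 90-100 | yes |
| 98 to 102 | +4 | 90-100 to >100 | yes |

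A patient with both readings below 90 falls in one of the nine cells, whatever the size of the fall. The three downward-shift cells (90-100 to <90, >100 to <90, >100 to 90-100) all need a Baseline of 90 mmHg or more.

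**Step 4: illustration only.** The documents give no diastolic distribution. Assuming a normal distribution, the share classed low is P(diastolic < 90) = Φ((90 - mean)/SD):

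| Assumed mean | SD 8 | SD 10 | SD 12 |
|---|---|---|---|
| 75 | 0.970 | 0.933 | 0.894 |
| 80 | 0.894 | 0.841 | 0.798 |
| 85 | 0.734 | 0.691 | 0.662 |
| 90 | 0.500 | 0.500 | 0.500 |

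Over this range 50% to 97% of readings would be classed low. Steps 1 to 3 do not depend on these assumptions.

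**The case against.** Five points can be made for leaving the text alone.

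- **The labels do not reach the output.** The shell prints only numeric ranges, so no table calls a reading low. This is correct, but the cut-points do reach the output, and removing the labels would still leave one undivided class below 90.
- **Any shift table hides movement within a class.** Systolic 139 to 91 also shows no shift. This is true, and a hidden within-class fall is not a fault in itself. The difference is that the bottom class is the one meant to isolate low values, and here it also takes in ordinary ones.
- **No low value is missed, since all lie below 90.** This stands as far as it goes: the fault is that the class does not discriminate. Rises across 90 and 100, and falls from 90 or above to below 90, remain visible.
- **The information is available elsewhere.** Table 14.3.1.4.1 gives diastolic mean, SD, median, range and change, and "Listing 16.2.8.3: Vital Signs" gives each patient's values. This stands and limits the harm. Neither output counts patients moving into a low class, which is the shift table's task.
- **Little hangs on it.** The shift table is an SAP addition, it covers two time points, and no test or stopping rule uses it. This also stands, and it is why the point is minor.

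**Conclusion.** The concern holds. The diastolic classes are inconsistent with the systolic classes beside them, the shell repeats the cut-points, and nothing else in either document repairs them. For low values the panel cannot do what the SAP says it is for.

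The size is small: one descriptive Baseline-to-Week 12 panel. The systolic and heart-rate classes, the continuous diastolic summaries, the listing and every efficacy analysis are unaffected.

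The conclusion rests only on the stated limits and on diastolic pressure being below systolic. The 50% to 97% range is an illustration under assumed means and SDs and carries no weight in the severity. The documents do not show how the error arose. A limit copied from the systolic line, or wrong labels on intended cut-points, are both possible.

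**What to change.** The sponsor should review and correct the diastolic class limits and labels in SAP Section 8.8.4.3 so that they are consistent with the systolic classes and can serve the stated purpose. The medical monitor should confirm them. The same limits then go into the diastolic rows and columns of the Table 14.3.1.4.2 shell. No replacement values are proposed here.

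The SAP Preface allows updates until the blind is broken, so the correction should be made before then; the documents do not show whether that point has passed. The cost is one line of SAP text and one panel of one shell, with no new data and no change to any other output.

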8.8.4.4 Physical Examination

Abnormal physical examination findings will be summarized by body system, visit, and treatment group. In addition to the summary, all physical examination findings will be listed.

8.8.4.5 Patient Global Impression of Treatment Side-Effects (PGI-SE)

Descriptive statistics by treatment group and visit will be provided for PGI-SE.

9. DETERMINATION OF SAMPLE SIZE

The following power calculations are based on the observed Week 12 results of the Phase 2 study, SGT-EBP01-09. This study was a three-arm trial including E-BPO cream, 1% and 5%, and vehicle in the treatment of rosacea. Estimates from the E-BPO cream, 5% arm were used in the power assessments. The anticipated randomization ratio is 2:1 for E-BPO cream, 5% and vehicle, respectively. The computations were performed with nQuery Advisor Version 7.0 using a two-sided test with a statistical significance value of 0.05.

A sample size of 86 in the E-BPO cream, 5% and 43 in the vehicle group has 95% power to detect a statistically significant difference in the proportion of patients who have at least a 2-grade reduction at Week 12 from Baseline in IGA and are clear or almost clear. The estimated percentages with a 2-grade reduction at Week 12 from Baseline in the IGA and clear or almost clear are 53.3% and 20.0% for the E-BPO cream and vehicle, respectively.

A sample size of 200 in the E-BPO cream, 5% and 100 in the vehicle group has 95% power to detect a statistically significant difference in inflammatory lesions. The estimated absolute change from Baseline in treatment means were -14.1 and -7.4 for E-BPO cream and vehicle, respectively, with a standard deviation (SD) of 6.70 and 17.24, respectively.

The sample sizes above will be increased to give a planned enrollment of 234 in the E-BPO cream, 5% group and 117 in the vehicle group since the Phase 3 trial is expected to enroll patients who are as a group more severe than those of the Phase 2 trial. This is a consequence of some changes in the inclusion criteria.

10. CHANGES IN THE PLANNED ANALYSES

There are no changes in the conduct of the study, but there are minor changes to the planned analyses.

Due to feedback received, the primary efficacy analysis was adjusted back to the original analysis. The modification to only use the non-parametric version as described in v4 of the protocol was not accepted by the agency. The original approach uses an ANCOVA analysis with the terms for treatment, analysis center, and Baseline count (and treatment-by-center interaction if the term is significant at 0.10). If the two-sided p-value for the skewness test is significant at 0.01, then the rank-transformed data will be used instead of nominal values. The original approach was accepted by the agency.

The pooling analysis described in the protocol is updated in the statistical analysis plan (SAP) to reflect the intended analysis. The protocol discusses pooling sites with five or fewer subjects enrolled in each treatment arm. Taking into consideration the randomization ratio, the SAP requires ten subjects in the active treatment arm and five subjects in the vehicle group.

As part of the pooling analysis, the treatment effect within investigational site must be investigated. The protocol states the site main effect will be examined by using a one-way analysis of variance (for lesion count variables) or a logistic regression analysis (for dichotomized IGA) with a factor of site. The SAP instead explains site will be incorporated into the primary analysis models. Change from Baseline in lesion counts will be analyzed with an ANCOVA (unranked or ranked) with factors of treatment group, investigational site and treatment group by investigational site interaction, and the respective Baseline lesion count variable as a covariate. The dichotomized primary endpoint will be analyzed with a logistic regression with factors of treatment group, investigational site and the interaction term of treatment group by investigational site.

The protocol describes repeated measures sensitivity analyses for the primary efficacy endpoints. Treatment group, analysis center and visit are listed as factors for the repeated measures analyses. In addition to these factors, the SAP includes a factor of treatment group by visit interaction.

The protocol describes imputing only Week 12 data with MCMC imputation, but all missing post-baseline data will be imputed. Only 2 seeds are needed for the MCMC imputation for inflammatory lesions (one seed for S5G4T-1 and one seed for vehicle) so only the Week 12 seeds from the protocol were used in the SAP. Only 2 seeds are needed for the MCMC imputation for IGA (one seed for S5G4T-1 and one seed for vehicle) so only the Week 12 seeds from the protocol were used in the SAP. Using only the Week 12 seed addresses concern from the FDA with regard to imputing data at each visit as the multiple seeds in the protocol suggests. Only one seed is needed for treatment group as PROC MI will impute data across the visits.

Geographic region was removed from the examination of subgroups as all sites in the study are in the United States.

Withdrawal by Subject	xx (xx.x%)	xx (xx.x%)	xx (xx.x%)
Study Terminated by Sponsor	xx (xx.x%)	xx (xx.x%)	xx (xx.x%)
Physician Decision	xx (xx.x%)	xx (xx.x%)	xx (xx.x%)
Worsening of Condition	xx (xx.x%)	xx (xx.x%)	xx (xx.x%)
Other	xx (xx.x%)	xx (xx.x%)	xx (xx.x%)

SOURCE: USERNAME\SPONSOR\PROJECT\JOBNAME (DATE,TIME)

Table 14.0.2.1: Summary of Subject Enrollment and Evaluability
(All Randomized Subjects)

	E-BPO 5% Cream (N=xxx)	Vehicle Cream (N=xxx)	Total (N=xxx)
Number of Randomized Subjects	xx	xx	xx
Number of Subjects Included in the ITT Population	xx (xx.x%)	xx (xx.x%)	xx (xx.x%)
Number of Subjects Excluded from the ITT Population	xx (xx.x%)	xx (xx.x%)	xx (xx.x%)
Reason Excluded from the ITT Population			
Not Dispensed Study Drug	xx (xx.x%)	xx (xx.x%)	xx (xx.x%)
Number of Subjects Included in the Safety Population	xx (xx.x%)	xx (xx.x%)	xx (xx.x%)
Number of Subjects Excluded from the Safety Population	xx (xx.x%)	xx (xx.x%)	xx (xx.x%)
Reasons Excluded from the Safety Population ^a			
No Documented use of Study Drug	xx (xx.x%)	xx (xx.x%)	xx (xx.x%)
No Post Baseline Safety Assessment	xx (xx.x%)	xx (xx.x%)	xx (xx.x%)
Number of Subjects Included in the PP Population	xx (xx.x%)	xx (xx.x%)	xx (xx.x%)
Number of Subjects Excluded from the PP Population	xx (xx.x%)	xx (xx.x%)	xx (xx.x%)
Reasons Excluded from the PP Population ^a			
Not Included in ITT Population	xx (xx.x%)	xx (xx.x%)	xx (xx.x%)
Violated Inclusion/Exclusion Criteria	xx (xx.x%)	xx (xx.x%)	xx (xx.x%)
Used Interfering Concomitant Medication	xx (xx.x%)	xx (xx.x%)	xx (xx.x%)
Did not Attend Week 12/ET Visit	xx (xx.x%)	xx (xx.x%)	xx (xx.x%)
Missed More Than 1 Post-Baseline Visit Prior to Week 12	xx (xx.x%)	xx (xx.x%)	xx (xx.x%)
Not Compliant with Dosing Regimen ^b	xx (xx.x%)	xx (xx.x%)	xx (xx.x%)
Week 12/ET Visit Out of Window (+/-4 days)	xx (xx.x%)	xx (xx.x%)	xx (xx.x%)
Other	xx (xx.x%)	xx (xx.x%)	xx (xx.x%)

^a Table includes primary reason (assigned in order presented in table) for reason subject was excluded.

^b Subjects lost to follow-up not included. A subject was considered compliant with the dosing regimen if the subject applied 80-120% of the expected number of applications and did not miss more than 5 consecutive applications while enrolled in the study.

SOURCE: USERNAME\SPONSOR\PROJECT\JOBNAME (DATE,TIME)

Table 14.0.2.2: Summary of Subject Evaluability by Analysis Center and Investigational Site
 (All Randomized Subjects)
 (Page 1 of xx)

Analysis Center	Investigational Site	Number Randomized	E-BPO 5% Cream			Vehicle Cream		
			ITT	PP	Safety	ITT	PP	Safety
xx	xx	xx	xx	xx	xx	xx	xx	xx
xx	xx	xx	xx	xx	xx	xx	xx	xx
	xx	xx	xx	xx	xx	xx	xx	xx
xx	xx	xx	xx	xx	xx	xx	xx	xx
xx	xx	xx	xx	xx	xx	xx	xx	xx
	xx	xx	xx	xx	xx	xx	xx	xx
	xx	xx	xx	xx	xx	xx	xx	xx

SOURCE: USERNAME\SPONSOR\PROJECT\JOBNAME (DATE,TIME)

Table 14.1.1.1: Summary of Subject Demographic Characteristics
(Intent-to-Treat Population)
(Page 1 of 2)

	E-BPO 5% Cream (N=xxx)	Vehicle Cream (N=xxx)	Total (N=xxx)
Age (years)			
n	xx	xx	xx
Mean	xx.x	xx.x	xx.x
SD	xx.xx	xx.xx	xx.xx
Median	xx.x	xx.x	xx.x
Min. to Max.	xx to xx	xx to xx	xx to xx
< Median (xx years)	xx (xx.x%)	xx (xx.x%)	xx (xx.x%)
≥ Median (xx years)	xx (xx.x%)	xx (xx.x%)	xx (xx.x%)
Sex			
n	xx	xx	xx
Male	xx (xx.x%)	xx (xx.x%)	xx (xx.x%)
Female	xx (xx.x%)	xx (xx.x%)	xx (xx.x%)
Ethnicity			
n	xx	xx	xx
Hispanic or Latino	xx (xx.x%)	xx (xx.x%)	xx (xx.x%)
Not Hispanic or Latino	xx (xx.x%)	xx (xx.x%)	xx (xx.x%)
Not Reported/Unknown	xx (xx.x%)	xx (xx.x%)	xx (xx.x%)

^a See Listing 16.2.4.1 for a complete list of other races.

SOURCE: USERNAME\SPONSOR\PROJECT\JOBNAME (DATE,TIME)

Table 14.1.1.1: Summary of Subject Demographics
(Intent-to-Treat Population)
(Page 2 of 2)

	E-BPO 5% Cream (N=xxx)	Vehicle Cream (N=xxx)	Total (N=xxx)
Race			
n	xx	xx	xx
American Indian or Alaska Native	xx (xx.x%)	xx (xx.x%)	xx (xx.x%)
Asian	xx (xx.x%)	xx (xx.x%)	xx (xx.x%)
Black or African American	xx (xx.x%)	xx (xx.x%)	xx (xx.x%)
Native Hawaiian or Other Pacific Islander	xx (xx.x%)	xx (xx.x%)	xx (xx.x%)
White	xx (xx.x%)	xx (xx.x%)	xx (xx.x%)
Multiple/Other ^a	xx (xx.x%)	xx (xx.x%)	xx (xx.x%)

^a See Listing 16.2.4.1 for a complete list of other races.

SOURCE: USERNAME\SPONSOR\PROJECT\JOBNAME (DATE,TIME)

Repeat Table 14.1.1.1 for the following tables:

Table 14.1.1.2: Summary of Subject Demographics (Per-Protocol Population)

Table 14.1.1.3: Summary of Subject Demographics (Safety Population)

Table 14.1.2.1: Subject Baseline Characteristics
(Intent-to-Treat Population)
(Page 1 of 2)

	E-BPO 5% Cream (N=xxx)	Vehicle Cream (N=xxx)	Total (N=xxx)
Height (cm)			
n	xx	xx	xx
Mean	xx.x	xx.x	xx.x
SD	xx.xx	xx.xx	xx.xx
Median	xx.x	xx.x	xx.x
Min. to Max.	xx to xx	xx to xx	xx to xx
Weight (kg)			
n	xx	xx	xx
Mean	xx.x	xx.x	xx.x
SD	xx.xx	xx.xx	xx.xx
Median	xx.x	xx.x	xx.x
Min. to Max.	xx to xx	xx to xx	xx to xx
BMI (kg/m²)			
n	xx	xx	xx
Mean	xx.x	xx.x	xx.x
SD	xx.xx	xx.xx	xx.xx
Median	xx.x	xx.x	xx.x
Min. to Max.	xx to xx	xx to xx	xx to xx

SOURCE: USERNAME\SPONSOR\PROJECT\JOBNAME (DATE,TIME)

Table 14.1.2.1: Subject Baseline Characteristics
(Intent-to-Treat Population)
(Page 2 of 2)

	E-BPO 5% Cream (N=xxx)	Vehicle Cream (N=xxx)	Total (N=xxx)
Inflammatory Lesion Count			
n	xx	xx	xx
Mean	xx.x	xx.x	xx.x
SD	xx.xx	xx.xx	xx.xx
Median	xx.x	xx.x	xx.x
Min. to Max.	xx to xx	xx to xx	xx to xx
Investigator Global Assessment			
n	xx	xx	xx
0 - Clear	xx (xx.x%)	xx (xx.x%)	xx (xx.x%)
1 – Almost Clear	xx (xx.x%)	xx (xx.x%)	xx (xx.x%)
2 - Mild	xx (xx.x%)	xx (xx.x%)	xx (xx.x%)
3 - Moderate	xx (xx.x%)	xx (xx.x%)	xx (xx.x%)
4 - Severe	xx (xx.x%)	xx (xx.x%)	xx (xx.x%)

SOURCE: USERNAME\SPONSOR\PROJECT\JOBNAME (DATE,TIME)

Repeat Table 14.1.2.1 for the following table:

Table 14.1.2.2: Subject Baseline Characteristics (Per-Protocol Population)

Table 14.1.2.3: Subject Baseline Characteristics (Safety Population)

Table 14.1.3.1: Summary of Medical History by System Organ Class and Preferred Term
(Intent-to-Treat Population)
(Page 1 of xx)

System Organ Class Preferred Term	E-BPO 5% Cream (N=xxx)		Vehicle Cream (N=xxx)		Total (N=xxx)	
	By Subject ^a	By Event ^b	By Subject ^a	By Event ^b	By Subject ^a	By Event ^b
Number (%) of Subjects Reporting at Least One Medical History Term	xx (xx.x%)	xx	xx (xx.x%)	xx	xx (xx.x%)	xx
System Organ Class	xx (xx.x%)	xx	xx (xx.x%)	xx	xx (xx.x%)	xx
Preferred Term	xx (xx.x%)	xx	xx (xx.x%)	xx	xx (xx.x%)	xx

^a Counts reflect number of subjects reporting one or more medical history terms that map to MedDRA. At each level of summarization (System Organ Class or Preferred Term) subjects are counted once. Percentages are based on the number of subjects in the safety population.

^b Counts reflect number of medical history terms that map to MedDRA.

Note: MedDRA Version 21.0

SOURCE: USERNAME\SPONSOR\PROJECT\JOBNAME (DATE,TIME)

{NOTE TO PROGRAMMER: The table will be sorted by overall descending frequency of SOC and then, within a SOC, by overall descending frequency of PT}

Repeat Table 14.1.3.1 for the following table:

Table 14.1.3.2: Summary of Medical History by System Organ Class and Preferred Term (Per-Protocol Population)

Table 14.1.3.3: Summary of Medical History by System Organ Class and Preferred Term (Safety Population)

Table 14.1.4.1: Summary of Prior Medications by ATC Level 2 and Preferred Name
(Safety Population)
(Page 1 of xx)

ATC Level 2 Term ^a Preferred Name	E-BPO 5% Cream (N=xxx)	Vehicle Cream (N=xxx)
Number (%) of Subjects Reporting at Least One Prior Medication	xx (xx.x%)	xx (xx.x%)
ATC Level 2 Term	xx (xx.x%)	xx (xx.x%)
Preferred Name	xx (xx.x%)	xx (xx.x%)

^a Counts reflect number of subjects reporting one or more medications that map to the WHO term. At each level of summarization (ATC Level 2 Term or Preferred Name) subjects are counted once. Percentages are based on the number of subjects in the safety population.

Note: WHO Drug Global Dictionary, Format B3, Version March 1, 2018
Prior medications are those used before the date of first study drug application.

SOURCE: USERNAME\SPONSOR\PROJECT\JOBNAME (DATE,TIME)

Table 14.1.4.2: Summary of Concomitant Medications by ATC Level 2 and Preferred Name
 (Safety Population)
 (Page 1 of xx)

ATC Level 2 Term ^a Preferred Name	E-BPO 5% Cream (N=xxx)	Vehicle Cream (N=xxx)
Number (%) of Subjects Reporting at Least One Concomitant Medication	xx (xx.x%)	xx (xx.x%)
ATC Level 2 Term Preferred Name	xx (xx.x%) xx (xx.x%)	xx (xx.x%) xx (xx.x%)

^a Counts reflect number of subjects reporting one or more medications that map to the WHO term. At each level of summarization (ATC Level 2 Term or Preferred Name) subjects are counted once. Percentages are based on the number of subjects in the safety population.

Note: WHO Drug Global Dictionary, Format B3, Version March 1, 2018
 Concomitant medications are those used on/after the date of first study drug application.

SOURCE: USERNAME\SPONSOR\PROJECT\JOBNAME (DATE,TIME)

Table 14.2.1.1: Pooling Analysis for Primacy Efficacy Endpoints
(Intent-to-Treat Population)

Endpoint	Investigational Site Pooling Analysis		Analysis Center Pooling Analysis	
	Skewness P-Value	Investigational Site by Treatment Group P-Value	Skewness P-Value	Analysis Center Treatment Group P-Value
Absolute Change from Baseline in Inflammatory Lesion Counts at Week 12	x.xxx ^c			
Ranked Analysis		x.xxx ^a		x.xxx ^e
Unranked Analysis		x.xxx ^b		x.xxx ^f
Achieving Clear or Almost Clear at Week 12	NA	x.xxx ^d	NA	x.xxx ^g

^a P-value for the interaction term from a ranked analysis of covariance with factors of treatment, investigational site, treatment by investigational site interaction and Baseline lesion count as a covariate.

^b P-value for the interaction term from an unranked analysis of covariance with factors of treatment, investigational site, treatment by investigational site interaction and Baseline lesion count as a covariate.

^c Skewness test, based on methods presented by J.H. Zar (1984), assessed for each imputed dataset. The average p-value is presented.

^d P-value for the interaction term from a logistic regression with factors of treatment, investigational site, treatment by investigational site interaction.

^e P-value for the interaction term from a ranked analysis of covariance with factors of treatment, analysis center, treatment by analysis center interaction and Baseline lesion count as a covariate.

^f P-value for the interaction term from an unranked analysis of covariance with factors of treatment, analysis center, treatment by analysis center interaction and Baseline lesion count as a covariate.

^g P-value for the interaction term from a logistic regression with factors of treatment, analysis center, treatment by analysis center interaction.

Note: Multiple imputation (MCMC) used to impute missing values.

SOURCE: USERNAME/SPONSOR/PROJECT/JOBNAME (DATE,TIME)

{NOTE TO PROGRAMMER: ADJUST FOOTNOTE “d” AND/OR “g” IF FIRTH’S PENALIZED LIKELIHOOD IS NEEDED}

Table 14.2.1.2: Primary Efficacy Analysis: Absolute Change from Baseline in Inflammatory Lesion Count and Dichotomized IGA Success at Week 12 (Intent-to-Treat Population)

	E-BPO 5% Cream (N=xxx)	Vehicle Cream (N=xxx)	Skewness P-Value	Treatment P-Value
Inflammatory Lesion Count – Absolute Change from Baseline				
LSMean ^a	xx.x	xx.x	x.xxx ^b	x.xxx ^a
LSSD ^a	xx.xx	xx.xx		x.xxx ^c
Achieving Clear or Almost Clear				
Success	xx.x%	xx.x%	N/A	x.xxx ^d
Failure	xx.x%	xx.x%		

^a Least squares means, standard deviations and treatment p-value from an analysis of covariance with factors of treatment group and analysis center and Baseline lesion count as a covariate. Negative least squares means values represent decrease from Baseline.

^b Skewness test, based on methods presented by J.H. Zar (1984), assessed for each imputed dataset. The average p-value is presented.

^c P-value from a ranked analysis of covariance with factors of treatment group and analysis center and Baseline lesion count as a covariate.

^d P-value from a logistic regression with factors of treatment group and analysis center.

Note: Multiple imputation (MCMC) used to impute missing values.

SOURCE: USERNAME\SPONSOR\PROJECT\JOBNAME (DATE, TIME)

{NOTE TO PROGRAMMER: ADJUST FOOTNOTE “d” IF FIRTH’S PENALIZED LIKELIHOOD IS NEEDED}

Repeat Table 14.2.1.2 for the following table:

Table 14.2.1.3: Primary Efficacy Analysis: Absolute Change from Baseline in Inflammatory Lesion Count and Dichotomized IGA Success at Week 12 (Per-Protocol Population)

Update footnote to “Note: Missing values imputed using last observation carried forward.”

Table 14.2.2.1.1: Summary of Inflammatory Lesion Counts at Each Evaluation
(Intent-to-Treat Population)
(Page 1 of 4)

Inflammatory Lesion Counts	E-BPO 5% Cream (N=xxx)	Vehicle Cream (N=xxx)
Baseline		
n	xx	xx
Mean	xx.x	xx.x
SD	xx.xx	xx.xx
Median	xx.x	xx.x
Min. to Max.	xx to xx	xx to xx
Week 2		
n	xx	xx
Mean	xx.x	xx.x
SD	xx.xx	xx.xx
Median	xx.x	xx.x
Min. to Max.	xx to xx	xx to xx
Change from Baseline		
n	xx	xx
Mean	xx.x	xx.x
SD	xx.xx	xx.xx
Median	xx.x	xx.x
Min. to Max.	xx to xx	xx to xx
Percent Change from Baseline		
n	xx	xx
Mean	xx.x	xx.x
SD	xx.xx	xx.xx
Median	xx.x	xx.x
Min. to Max.	xx to xx	xx to xx

Note: Multiple imputation (MCMC) used to impute missing values. Summary statistics for Weeks 2, 4, 8, and 12 represent average values, obtained from averaging the summary statistics generated from each imputed dataset.

SOURCE: USERNAME\SPONSOR\PROJECT\JOBNAME (DATE,TIME)

Table 14.2.2.1.1: Summary of Inflammatory Lesion Counts at Each Evaluation
(Intent-to-Treat Population)
(Page 2 of 4)

Inflammatory Lesion Counts	E-BPO 5% Cream (N=xxx)	Vehicle Cream (N=xxx)
Week 4		
n	xx	xx
Mean	xx.x	xx.x
SD	xx.xx	xx.xx
Median	xx.x	xx.x
Min. to Max.	xx to xx	xx to xx
 Change from Baseline		
n	xx	xx
Mean	xx.x	xx.x
SD	xx.xx	xx.xx
Median	xx.x	xx.x
Min. to Max.	xx to xx	xx to xx
 Percent Change from Baseline		
n	xx	xx
Mean	xx.x	xx.x
SD	xx.xx	xx.xx
Median	xx.x	xx.x
Min. to Max.	xx to xx	xx to xx

Note: Multiple imputation (MCMC) used to impute missing values. Summary statistics for Weeks 2, 4, 8, and 12 represent average values, obtained from averaging the summary statistics generated from each imputed dataset.

SOURCE: USERNAME/SPONSOR/PROJECT/JOBNAME (DATE,TIME)

Table 14.2.2.1.1: Summary of Inflammatory Lesion Counts at Each Evaluation
(Intent-to-Treat Population)
(Page 2 of 4)

Inflammatory Lesion Counts	E-BPO 5% Cream (N=xxx)	Vehicle Cream (N=xxx)
Week 8		
n	xx	xx
Mean	xx.x	xx.x
SD	xx.xx	xx.xx
Median	xx.x	xx.x
Min. to Max.	xx to xx	xx to xx
Change from Baseline		
n	xx	xx
Mean	xx.x	xx.x
SD	xx.xx	xx.xx
Median	xx.x	xx.x
Min. to Max.	xx to xx	xx to xx
Percent Change from Baseline		
n	xx	xx
Mean	xx.x	xx.x
SD	xx.xx	xx.xx
Median	xx.x	xx.x
Min. to Max.	xx to xx	xx to xx

Note: Multiple imputation (MCMC) used to impute missing values. Summary statistics for Weeks 2, 4, 8, and 12 represent average values, obtained from averaging the summary statistics generated from each imputed dataset.

SOURCE: USERNAME/SPONSOR/PROJECT/JOBNAME (DATE,TIME)

Table 14.2.2.1.1: Summary of Inflammatory Lesion Counts at Each Evaluation
(Intent-to-Treat Population)
(Page 4 of 4)

Inflammatory Lesion Counts	E-BPO 5% Cream (N=xxx)	Vehicle Cream (N=xxx)
Week 12		
n	xx	xx
Mean	xx.x	xx.x
SD	xx.xx	xx.xx
Median	xx.x	xx.x
Min. to Max.	xx to xx	xx to xx
Change from Baseline		
n	xx	xx
Mean	xx.x	xx.x
SD	xx.xx	xx.xx
Median	xx.x	xx.x
Min. to Max.	xx to xx	xx to xx
Percent Change from Baseline		
n	xx	xx
Mean	xx.x	xx.x
SD	xx.xx	xx.xx
Median	xx.x	xx.x
Min. to Max.	xx to xx	xx to xx

Note: Multiple imputation (MCMC) used to impute missing values. Summary statistics for Weeks 2, 4, 8, and 12 represent average values, obtained from averaging the summary statistics generated from each imputed dataset. Negative values represent decrease from Baseline.

SOURCE: USERNAME/SPONSOR/PROJECT\JOBNAME (DATE,TIME)

Repeat Table 14.2.2.1.1 for the following table:

Table 14.2.2.1.2: Summary of Inflammatory Lesion Counts at Each Evaluation (Per-Protocol Population)

Change footnote to “Note: Missing values imputed using last observation carried forward. Negative values represent decrease from Baseline.”

Table 14.2.2.2: Summary of Absolute Change in Inflammatory Lesion Counts at Week 12 by Analysis Center
(Intent-to-Treat Population)

Analysis Center (Investigational Sites)	E-BPO 5% Cream (N=xxx)			Vehicle Cream (N=xxx)		
	n	Mean	SD	n	Mean	SD
xx (y, z)	xx	xx.x	xx.xx	xx	xx.x	xx.xx
xx (y, z)	xx	xx.x	xx.xx	xx	xx.x	xx.xx
xx (y, z)	xx	xx.x	xx.xx	xx	xx.x	xx.xx
xx (y, z)	xx	xx.x	xx.xx	xx	xx.x	xx.xx
xx (y, z)	xx	xx.x	xx.xx	xx	xx.x	xx.xx
xx (y, z)	xx	xx.x	xx.xx	xx	xx.x	xx.xx
xx (y, z)	xx	xx.x	xx.xx	xx	xx.x	xx.xx
xx (y, z)	xx	xx.x	xx.xx	xx	xx.x	xx.xx
xx (y, z)	xx	xx.x	xx.xx	xx	xx.x	xx.xx

Note: Multiple imputation (MCMC) used to impute missing values. Summary statistics represent average values, obtained from averaging the summary statistics generated from each imputed dataset. Negative values represent decrease from Baseline.

SOURCE: USERNAME\SPONSOR\PROJECT\JOBNAME (DATE, TIME)

Table 14.2.3.1.1: Summary of Investigator Global Assessment at Each Evaluation
(Intent-to-Treat Population)
(Page 1 of 4)

Investigator Global Assessment	E-BPO 5% Cream (N=xxx)	Vehicle Cream (N=xxx)
Baseline		
n	xx	xx
0 - Clear	xx (xx.x%)	xx (xx.x%)
1 - Almost Clear	xx (xx.x%)	xx (xx.x%)
2 - Mild	xx (xx.x%)	xx (xx.x%)
3 - Moderate	xx (xx.x%)	xx (xx.x%)
4 - Severe	xx (xx.x%)	xx (xx.x%)
Week 2		
0 - Clear	xx.x%	xx.x%
1 - Almost Clear	xx.x%	xx.x%
2 - Mild	xx.x%	xx.x%
3 - Moderate	xx.x%	xx.x%
4 - Severe	xx.x%	xx.x%
Achieving Clear or Almost Clear		
Success	xx.x%	xx.x%
Failure	xx.x%	xx.x%

Note: Multiple imputation (MCMC) used to impute missing values. Percentages for Weeks 2, 4, 8, and 12 represent average values, obtained from averaging the summary statistics generated from each imputed dataset.

SOURCE: USERNAME/SPONSOR/PROJECT/JOBNAME (DATE,TIME)

Table 14.2.3.1.1: Summary of Investigator Global Assessment at Each Evaluation
(Intent-to-Treat Population)
(Page 2 of 4)

Investigator Global Assessment	E-BPO 5% Cream (N=xxx)	Vehicle Cream (N=xxx)
Week 4		
0 - Clear	xx.x%	xx.x%
1 - Almost Clear	xx.x%	xx.x%
2 - Mild	xx.x%	xx.x%
3 - Moderate	xx.x%	xx.x%
4 - Severe	xx.x%	xx.x%
 Achieving Clear or Almost Clear		
Success	xx.x%	xx.x%
Failure	xx.x%	xx.x%

Note: Multiple imputation (MCMC) used to impute missing values. Percentages for Weeks 2, 4, 8, and 12 represent average values, obtained from averaging the summary statistics generated from each imputed dataset.

SOURCE: USERNAME\SPONSOR\PROJECT\JOBNAME (DATE,TIME)

Table 14.2.3.1.1: Summary of Investigator Global Assessment at Each Evaluation
(Intent-to-Treat Population)
(Page 3 of 4)

Investigator Global Assessment	E-BPO 5% Cream (N=xxx)	Vehicle Cream (N=xxx)
Week 8		
0 - Clear	xx.x%	xx.x%
1 - Almost Clear	xx.x%	xx.x%
2 - Mild	xx.x%	xx.x%
3 - Moderate	xx.x%	xx.x%
4 - Severe	xx.x%	xx.x%
 Achieving Clear or Almost Clear		
Success	xx.x%	xx.x%
Failure	xx.x%	xx.x%

Note: Multiple imputation (MCMC) used to impute missing values. Percentages for Weeks 2, 4, 8, and 12 represent average values, obtained from averaging the summary statistics generated from each imputed dataset.

SOURCE: USERNAME\SPONSOR\PROJECT\JOBNAME (DATE,TIME)

Table 14.2.3.1.1: Summary of Investigator Global Assessment at Each Evaluation
(Intent-to-Treat Population)
(Page 4 of 4)

Investigator Global Assessment	E-BPO 5% Cream (N=xxx)	Vehicle Cream (N=xxx)
Week 12		
0 - Clear	xx.x%	xx.x%
1 - Almost Clear	xx.x%	xx.x%
2 - Mild	xx.x%	xx.x%
3 - Moderate	xx.x%	xx.x%
4 - Severe	xx.x%	xx.x%
 Achieving Clear or Almost Clear		
Success	xx.x%	xx.x%
Failure	xx.x%	xx.x%

